5.4 Justification – Risk-Benefit

The hypothesis is that the proposed treatment regime will rebalance islet cell interactions and the pancreatic immune environment to increase beta cell function and limit the autoimmune reaction. This will improve blood sugar control and at the same create a more fertile field for the GAD65 antigen specific immunotherapy Diamyd to induce long term tolerability. Administering Diamyd directly into lymph nodes may enhance the tolerizing effect even more (see rationale in section 4.3).

The individual risks of Diamyd and oral vitamin D are not expected to be increased by combining them in the proposed manner.

The justification for the proposed study with the combination treatment regimen, combined with the proposed exclusion and inclusion criteria and 15-months follow-up investigate if the combination of Diamyd and vitamin D slow down or halt the progress of autoimmune beta cell destruction in T1D, aiming to preserve blood glucose control and endogenous insulin secretion and thereby possibly reduce both acute and long-term complication of the disease. As Diamyd has proven to be well tolerated in a large number of patients in previous studies, the possibility of therapeutic benefit outweighs the risks. In order to safeguard the patients, a DSMB will review data from the study twice a year.

6 TRIAL OBJECTIVES AND PURPOSE

6.1 Aim of Present Study

The main goal is to find a reasonably safe and tolerable treatment for young and adult patients with T1D which can preserve residual insulin secretion, improve the patients' quality of life (QoL) and reduce the risk of both short- and long term complications.

6.2 Primary Objective

The primary objective is to evaluate the efficacy of Diamyd, administered into lymph nodes in combination with an oral vitamin D regimen, compared to placebo in terms of preserving endogenous insulin secretion as measured by C-peptide.

6.3 Secondary Objectives

The secondary objectives are to compare Diamyd, administered into lymph nodes in combination with an oral vitamin D regimen and placebo treatment with respect to the effects on the diabetes status, treatment safety, immune system and quality of life (QoL) of the patients.

6.4 Endpoints

6.4.1 Primary Endpoint

The primary endpoint in this study is:

- Change in C-peptide ($AUC_{\text{mean } 0-120 \text{ min-}}$) during a Mixed Meal Tolerance Test (MMTT) between baseline and 15 months.

6.4.2 Secondary Endpoints

The key secondary endpoints to evaluate diabetic status are:

- Change in insulin-dose-adjusted HbA1c (IDAA1c) between baseline and 15 months.
- Change in HbA1c between baseline and 15 months.
- Change in daily exogenous insulin consumption between baseline and 15 months.

The other secondary endpoints to evaluate diabetic status are:

- Change in glycemic variability/fluctuations (evaluated from data from continuous glucose monitoring FreeStyle LibrePro, Flash Glucose Monitoring [FGM]) over 14 day period between Screening and 15 months.
- Proportion of patients with $IDAA1c \leq 9$ at 15 months.
- Proportion of patients with a stimulated maximum C-peptide level above 0.2 nmol/L (0.6 ng/ml) at 15 months.
- Proportion of patients with a stimulated 90min C-peptide level above 0.2 nmol/L (0.6 ng/ml) at 15 months.
- Number of self-reported episodes of severe hypoglycemia (Severe hypoglycemia defined as needing help from others and/or seizures and/or unconscious) between baseline and 15 months.
- Change in Rate of hypoglycemic events between baseline and 15 months.

- Number of patients having at least 1 severe hypoglycemic event between baseline and 15 months.
- Change in maximum C-peptide during MMTT between baseline and 15 months.
- Change in Fasting C-peptide between baseline and 15 months.
- C-peptide measured at 30, 60, 90, and 120 minutes during MMTT at 15 months.
- Change in body weight and body mass index (BMI) between baseline and 15 months

The secondary endpoints to evaluate safety are:

- Injection site reactions
- Occurrence of AEs
- Laboratory measurements (hematology and clinical chemistry)
- Urine analysis (microalbuminuria, creatinine)
- Physical examinations, including neurological assessments
- GAD65A titer
- Vital signs (blood pressure [BP])

The secondary endpoints to evaluate the influence on the immune system are:

- Concentrations of serum autoantibodies towards GAD65 and IA-2.
- Concentrations of serum autoantibody isotypes towards GAD65.
- Secretion of cytokines interleukin (IL)-1, IL-2, IL-5, IL-13, IL-10, IL-17, interferon (IFN) γ , and tumour necrosis factor (TNF) α by peripheral blood mononuclear cells (PBMCs) upon stimulation with GAD65.
- Serum concentrations of cytokines IL-1, IL-2, IL-5, IL-13, IL-10, IL-17, IFN γ , and TNF α .
- Secretion of cytokines IL-1, IL-2, IL-5, IL-13, IL-10, IL-17, IFN γ , and TNF α by PBMCs upon stimulation with anti-CD3 and anti-CD28.
- Proliferation of PBMCs upon stimulation with GAD65.
- Further exploratory immunological characterization.

The secondary endpoints of Quality of Life are:

- Change in QoL as measured by questionnaire EQ-5D-5L between baseline and Month 15.
- Quality adjusted life years (QALYs) based on the EQ-5D-5L questionnaire.

6.4.3 Exploratory Endpoints

All data collected at the 24-month follow-up visit (Visit 8) will be regarded as exploratory endpoints and will be presented using summary statistics including data from the main study period where only the patients that participated in the Extended Study Period will be included. The following statistical analyses will be repeated for the whole study period:

- The change in log-transformed C-peptide $AUC_{\text{mean } 0-120 \text{ min}}$ during an MMTT from baseline to Month 24

- Change in HbA1c between baseline and 24 months
- Change in daily exogenous insulin consumption between baseline and 24 months
- Change in Fasting C-peptide between baseline and 24 months.
- Change in glycemic variability/fluctuations (evaluated from data from continuous glucose monitoring FreeStyle LibrePro, FGM) over 14 day period between Screening and 24 months.
- Rate of hypoglycemic events using Poisson regression including randomization strata (GAD65A)
- Number of patients having at least 1 severe hypoglycemic event using Cochran/Mantel-Haenszel Test stratified for randomization strata (GAD65A)
- Change in body weight and body mass index (BMI) between baseline and 24 months

7 TRIAL DESIGN

7.1 Description of the Study Design and Procedures

The study is a 2-arm, randomized, double-blind, placebo-controlled study in GAD65A positive T1D patients aged ≥ 12 and < 25 years old, diagnosed within 6 months prior to screening with fasting C-peptide levels ≥ 0.12 nmol/L (0.36 ng/ml). In total, the aim is to recruit 106 patients at approximately 22 sites. The patients will be followed for 15 months with 7 visits to the clinic (Table 2) in the Main Study Period. All patients that are ongoing, i.e. have not performed Visit 7 (Month 15) when protocol version 7 is approved and implemented, will be asked to participate in the Extension Study Period which include Visit 8 at month 24 (Table 3).

Patients and parent(s)/guardian(s), as applicable, will provide written informed consent before any study-related procedures are performed. On Day 1 (Visit 2), 2-4 weeks after the Screening Visit, patients eligible for the study will be randomized in a 1:1 ratio stratified by GAD65A level and country to receive either:

- i) three (3) intralymphatic injections with 4 μ g Diamyd on Days 30, 60, and 90 and; ii) oral vitamin D 2000 IE daily for 4 months (from Day 1 through Day 120)
- i) three (3) intralymphatic injections of Placebo for Diamyd on Days 30, 60, and 90 and; ii) oral Placebo for vitamin D daily for 4 months (from Day 1 through Day 120)

The treatment schedule is given in Table 1.

At the screening visit patients will be assigned a 3-digit country/site number and a 3-digit sequential screening number and these numbers together will be used as a 6-digit patient identification (Patient Number), i.e. XXX-YYY.

Individual patients will be exposed to Diamyd for a maximum of 3 months and vitamin D for a maximum of 4 months. All patients will continue to receive intensive insulin treatment from their personal physicians during the whole study period. All patients will be monitored for at least 1 hour after administration of each Diamyd/placebo injection.

When the last patient has completed the double-blind study period, the study code will be broken and results analyzed.

Table 1 Schedule of Patient Visits for DIAGNODE-2

	Main Study Period							Extension Study Period
	Screening	Intervention and Follow-up						Follow-up
	Day -14 to -28 Screening	Day 1 Baseline	Day 30 Month 1 ±5 days	Day 60 Month 2 ±5 days	Day 90 Month 3 ±5 days	Day 180 Month 6 ±14 days	Day 450 Month 15 ±14 days	Day 720** Month 24 ±14 days
	Visit 1	Visit 2	Visit 3	Visit 4	Visit 5	Visit 6	Visit 7	Visit 8
Active			Diamyd 4 µg intra- lymphatic injection	Diamyd 4 µg intra- lymphatic injection	Diamyd 4 µg intra- lymphatic injection			
		Vitamin D 2000 IE daily, administered orally during 4 months (Day 1 to day 120)*						
Placebo			Placebo for Diamyd, intra- lymphatic injection	Placebo for Diamyd, intra- lymphatic injection	Placebo for Diamyd, intra- lymphatic injection			
		Placebo for vitamin D daily, administered orally during 4 months (Day 1 to day 120)*						

*Treatment with vitamin D/placebo starts at Visit 2 if the Vitamin D serum levels are below 100 nmol/L (40 ng/ml) at screening.

If the patient has Vitamin D serum levels above 100 nmol/L (40 ng/ml) at screening, no Vitamin D/placebo treatment will be given for that patient and only Diamyd/placebo injections will be given.

**Patients that are ongoing, i.e. have not performed Visit 7 when protocol version 7 (Month 15) is approved and implemented, will be asked to participate in the Extension Study Period which include Visit 8 at Month 24.

Table 2 Schedule of Study Events, Main Study Period

Event	V1 Screening	V2 Baseline Visit	V3 Month 1	V4 ^a Month 2	V5 ^a Month 3	V6 Month 6	V7 ^a Month 15
DAY	-14 to -28	1	30 (±5)	60 (±5)	90 (±5)	180 (±14)	450 (±14)
Informed Consent	X						
Eligibility check ^b	X	X					
Demographics	X						
Randomization		X					
Diamyd/placebo ^a			X ^c	X ^c	X ^c		
Vitamin D/placebo ^d start /end		X				X (day 120)	
Medical History	X						
Family history of T1D	X						
General Physical Exam ^e	X	X	X	X	X	X	X
Neurological Assessment	X	X	X	X	X	X	X
Concomitant Medication	X	X	X	X	X	X	X
Vital signs (BP)	X	X	X	X	X	X	X
Pubertal Stage, if applicable ^f	X					X	X
Distribution of patient eDiary		X					
eDiary use compliance			X	X	X	X	X
Injection Site Inspection; investigator/study nurse ^g			X	X	X		
Injection Site Inspection; in eDiary ^h			X	X	X		
Insulin Dose Collected ⁱ		X	X	X	X	X	X
FreeStyle LibrePro, FGM ^j	X					X	X
AEs		X	X	X	X	X	X
Urine Pregnancy Test (menarchal females only)	X	X	X	X	X	X	X
Self-reported severe hypoglycemia ^k		X	X	X	X	X	X
QoL questionnaire		X				X	X
MMTT ^l		X				X	X
Blood Sampling for Safety, Genetics, Vitamin D levels and Immunology:							
Hematology	X	X	X	X	X	X	X
Clinical Chemistry	X	X	X	X	X	X	X
GAD65A titer	X	X	X	X	X	X	X
HLA characterization			X				
Vitamin D level	X	X	X	X	X	X	X
Covid-19 serological test^m							X
Other immunological parameters as specified in Section 6.4.2		X	X	X	X	X	X
Urine Analysis:							
Microalbuminuria	X	X	X	X	X	X	X
Creatinine	X	X	X	X	X	X	X
Blood Sampling for Diabetes Status:							
Fasting C-peptide	X	X	X	X	X	X	X
MMTT-induced C-peptide^l		X				X	X
HbA1c	X	X	X	X	X	X	X
Fasting Glucose	X	X	X	X	X	X	X
MMTT-induced Glucose^l		X				X	X

Abbreviations: AEs=Adverse Events; BP= Blood Pressure; eDiary=electronic Diary; GAD65A=Antibodies to glutamic acid decarboxylase with molecular mass 65kDa; HBA1c=Hemoglobin A1c; HLA=Histocompatibility antigen; MMTT=mixed meal tolerance test; FGM=Flash Glucose Monitoring; GAD65=Glutamine acid decarboxylase with a molecular mass of 65kDa; GAD65A= antibodies to GAD65; MMTT=Mixed Meal Tolerance Test; T1D=Type 1 Diabetes; QoL=Quality of Life

- a. Study drug administration: For Visit 4 and 5 the visit date must be set in accordance with Visit 3 and 4, respectively, so that the first, second and third doses will be 30 days apart (\pm 5days).
- b. If the fasting c-peptide concentration is not $\geq 0,12$ nmol/L (0.36 ng/ml) at the screening visit this test can be repeated on another day within a period of 2 weeks (maximum 2 tests on different days within a 2-week period).
- c. The Diamyd/placebo injection directly into the inguinal lymph node is to be done by an appropriately qualified person at the X-ray department by help of ultrasound technique. For more information regarding the injection please refer to the operations manual for the injection procedure.
- d. Treatment with vitamin D/placebo starts at Visit 2 if the Vitamin D serum levels are below 100 nmol/L (40 ng/ml) at screening. If the patient has Vitamin D serum levels above 100 nmol/L (40 ng/ml) at screening, no Vitamin D/placebo treatment will be given for that patient.
- e. General Physical Exam also to include height and weight
- f. Pubertal Stage should be measured when applicable. Not applicable >1 5 years after the patient have reached final height
- g. The investigator/study nurse will inspect the injection site before and after the injection is given and record any injection site reactions in the electronic Case Report Form (eCRF)
- h. The patient will record injection site reactions in the eDiary starting the day after injection and for 7 days following the injection. Injection site reactions reported by patients in the eDiary during day 1-7 following an injection should not be reported as an AE in the eCRF. Any injections site reactions reported after the 1 week recording period will be recorded as AEs in the eCRF.
- i. Patients will record insulin dose in the eDiary for 4 days prior each visit starting from Visit 2. Insulin dose collected at Visit 2 (for the 4 days prior to Visit 2) will be done by the Investigator and recorded in the eCRF.
- j. FGM during 2 weeks post visit for Visits 1, 6 and 7. Patients will be given instructions on when and where to return the device after the testing period. For instruction on how to return the Freestyle Libre Pro sensor, please refer to the Freestyle Libre Pro Worksheet.
- k. The number of self-reported severe hypoglycemia (defined as needing help from others and/or seizures and/or unconsciousness) should be recorded in the eCRF and each event will be recorded separately.
- l. See Procedure for MMTT in the Operations Manual
- m. Only applicable to patients completing their Visit 7 after 01 January 2020.
- n. Patients that have completely withdrawn from the study will be asked to return for a final visit at month 15, in order to achieve as complete as possible follow-up. See section 8.5 for further details.

Table 3 Schedule of Study Events, Extension Study Period

Event	V8 ^g Month 24
DAY	720 (±14)
General Physical Exam ^a	X
Neurological Assessment	X
Concomitant Medication	X
Vital signs (BP)	X
Pubertal Stage, if applicable ^b	X
eDiary use compliance	X
Insulin Dose Collected ^c	X
FreeStyle LibrePro, FGM ^d	X
AEs	X
Urine Pregnancy Test (menarchal females only)	X
Self-reported severe hypoglycemia ^e	X
QoL questionnaire	X
MMTT ^f	X
Blood Sampling for Safety, Genetics, Vitamin D levels and Immunology:	
Hematology	X
Clinical Chemistry	X
GAD65A titer	X
Vitamin D level	X
Covid-19 serological test	X
Other immunological parameters as specified in Section 6.4.2	X
Urine Analysis:	
Microalbuminuria	X
Creatinine	X
Blood Sampling for Diabetes Status:	
Fasting C-peptide	X
MMTT-induced C-peptide^f	X
HbA1c	X
Fasting Glucose	X
MMTT-induced Glucose^f	X

Abbreviations: AEs=Adverse Events; BP= Blood Pressure; eDiary=electronic Diary; GAD65A=Antibodies to glutamic acid decarboxylase with molecular mass 65kDa; HBA1c=Hemoglobin A1c; HLA=Histocompatibility antigen; MMTT=mixed meal tolerance test; FGM=Flash Glucose Monitoring; GAD65=Glutamine acid decarboxylase with a molecular mass of 65kDa; GAD65A= antibodies to GAD65; MMTT=Mixed Meal Tolerance Test; T1D=Type 1 Diabetes; QoL=Quality of Life

- General Physical Exam also to include height and weight
- Pubertal Stage should be measured when applicable. Not applicable >1.5 years after the patient have reached final height
- Patients will record insulin dose in the eDiary for 4 days prior each visit starting from Visit 2.
- FGM for 2 weeks post visit for Visits 8 (for patients participating in this extra follow-up visit). Patients will be given instructions on when and where to return the device after the testing period. For instruction on how to return the Freestyle Libre Pro sensor, please refer to the Freestyle Libre Pro Worksheet.
- The number of self-reported severe hypoglycemia (defined as needing help from others and/or seizures and/or unconsciousness) should be recorded in the eCRF and each event will be recorded separately. See Procedure for MMTT in the Operations Manual

- f. See Procedure for MMTT in the Operations Manual
- g. Patients that are ongoing, i.e. have not performed Visit 7 (Month 15) when protocol version 7 is approved and implemented, will be asked to consent for the Extension Study Period an additional visit at Month 24.

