7.2 Patient Diary

The patients will be supplied with an eDiary at Visit 2. The diary will be internet based and the patients will be able to access the diary from either a computer or a smart phone. From Visit 3 until Visit 8 the patient will record insulin doses 4 days before each visit (at Visit 2 the insulin dose will be collected at the visit and will be done by the Investigator and recorded in the eCRF). The patient will also use the eDiary for documentation of injection site reactions during the week following injection (Visits 3, 4 and 5), starting the day after the injection.

The patient will be carefully instructed by study personnel on how to log in and complete the eDiary. The investigator/study nurse will review the eDiaries at each visit to check that the patient is completing the eDiary as instructed. Injection site reactions reported by patients in the eDiary during day 1-7 following an injection should not be reported as AEs in the eCRF.

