11 ADVERSE EVENTS

11.1 Definitions of Adverse Events (AE)

An AE is defined as any untoward medical occurrence in a subject during a clinical study administered a medicinal product and which does not necessarily have a causal relationship with this treatment(s).

An AE can therefore be any unfavorable and unintended clinical sign or symptom, any illness or disease, which develops or worsens in intensity during the course of the trial. It also includes an abnormal laboratory finding, if e.g., the abnormality results in trial withdrawal, is serious, is associated with clinical signs or symptoms, or is considered being of clinical relevance.

It could also include accidents and reasons for changes in medication (drug and/or dose), any medical/nursing/pharmacy consultation and admission to hospital/surgical operations.

Any new findings, clinically significant laboratory values or worsening of pre-existing condition must be reported as an AE by the investigator, whether or not considered related to the medicinal product(s).

Note that hospital admission and/or surgical operations for illness, which existed before the study drug was given or the subject was enrolled in the clinical trial and did not worsen during the study, are not AEs.

T1D-related events

The number of self-reported episodes of severe hypoglycemia (Severe hypoglycemia defined as needing help from others and/or seizures and/or unconscious) between baseline and subsequent visits will be collected in the eCRF. Hypoglycemia, changes in C-peptide, changes to insulin dosage, and increases in HbA1c/blood glucose will not be reported as AEs unless the definition of SAEs is met.

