11.5 Reporting of Adverse Events

All AEs must be recorded in the eCRF, defining relationship to study medication, intensity, seriousness, action taken with study drug, and outcome. AEs should also be recorded by the investigator in the patient file/notes.

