13.2.3.3.1 Secondary Safety Variables

Adverse events:

AEs will be coded according to the MedDRA system and tabulated by System Organ Class (SOC) and by preferred term.

A summary table will be presented with total number and No. of patients with:

- AEs
- serious AEs
- related AEs
- AE leading to discontinuation

AE will only be counted once within each patient on a preferred term level.

The total number of patients with at least one AE and the number of AEs will be derived and summarized by SOC and preferred term.

AEs will also be tabulated versus intensity and relationship to treatment (classified as related for outcomes “Remote”, “Plausible” and “Probable” and not related for outcome “Unrelated”. If a patient has more than one event classified with the same preferred term, then the worst intensity and the worst relationship will be used. In this table, patients having AEs will be identified by their patient number.

A treatment-emergent AE (TEAE) is an event emerging after treatment start or worsening during treatment. Hence, events with an onset time on or after the time of treatment start are treatment-emergent. Only TEAEs will be included in summary tables. Pre-treatment AEs will be listed.

Treatment-emergent serious adverse events (TESAEs) will be listed separately.

In listings of AEs the relative day of occurrence will be given. Relative day will be calculated as (Date of first administration of IMP – AE start date) + 1 for AEs occurring on date of first administration of IMP or later and as (Date of first administration of IMP – AE start date), otherwise.

AEs will be presented for the main study period and for the whole study period.

Other safety endpoints:

All other safety endpoints will be presented using summary statistics. These presentations will be done for the Main Study Period and the whole study period where only the patients that participated in the Extension Study Period will be included. For laboratory measurements and vital signs change from baseline will also be summarized. Shift tables will present shifts for all endpoints for which normal/abnormal (Not Clinically Significant/Clinically Significant [NCS/CS]) judgements exist.

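### The rule keeping first-week eDiary injection site reactions off the AE page has no exception, conflicts with Sections 10.4 and 11.5, and can leave the discontinuation table short

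*Protocol*

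**What the plan says.** The recording rule stands twice in the protocol. Footnote h to Table 2 (Section 7.1) says that injection site reactions "reported by patients in the eDiary during day 1-7 following an injection should not be reported as an AE in the eCRF". Section 7.2 says the same: "Injection site reactions reported by patients in the eDiary during day 1-7 following an injection should not be reported as AEs in the eCRF". The diary window opens the day after the injection and runs for 7 days. Once it has closed, the treatment of the same event reverses: "Any injections site reactions reported after the 1 week recording period will be recorded as AEs in the eCRF".

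Section 11.5 sets the general rule: "All AEs must be recorded in the eCRF, defining relationship to study medication, intensity, seriousness, action taken with study drug, and outcome". Section 10.4 adds that when a medication is started or changed because of a new or worsening condition, that condition has to be entered as an AE. Section 11.6 requires an SAE form for every SAE, related or not.

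The protocol has one other exclusion of this type. Section 11.1 says that hypoglycaemia and other diabetes-related changes "will not be reported as AEs unless the definition of SAEs is met".

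On the output side, Section 13.2.3.3.1 plans summaries of related AEs and of "AE leading to discontinuation", and a tabulation by intensity and relationship. Section 8.5 lists unacceptable AEs among the standard reasons for stopping study product.

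**The concern.** Keeping routine local reactions in a diary is a sensible design. The difficulty is that the exclusion is absolute, while other sections give the opposite instruction for particular kinds of reaction. A site that follows footnote h literally would leave the AE page blank for a first-week reaction that was treated, was serious, or ended the injections.

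Two things are at stake. First, sites hold contradictory instructions, so the same event may be entered differently from one centre to the next. Second, the AE tables could show no discontinuation for a local reaction when one had occurred. Section 5.1 supports tolerability partly by stating that no earlier patient left treatment because of such a reaction. This trial's AE tables could not be relied on to test that statement for the intralymphatic route.

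This is a rule about data collection. Seriousness, causality for each product and action taken are attached to AE records (Sections 11.4 and 11.5), and the protocol does not say that the eDiary captures them. An analysis plan cannot tabulate what was not recorded.

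**Working it through.** There is no figure of the plan's to reproduce. The check takes one kind of event at a time and reads off what each section tells the site to do.

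1. **Mild reaction on day 3, untreated.** Footnote h and Section 7.2: diary only. Section 11.5: AE page. The texts conflict, but the intention is clear and the loss is harmless.
2. **Reaction on day 3 for which a new medication is started.** Footnote h and Section 7.2: not an AE entry. Section 10.4: must be an AE entry. This is a direct contradiction.
3. **Serious reaction on day 3.** Section 11.6: SAE form. Footnote h and Section 7.2: no AE entry. Section 12.1 compares the SAEs in the safety database with those in the study database before closure. The case would be in the first and, read literally, not in the second, so it would surface as a mismatch.
4. **Non-serious reaction on day 3 after which injections stop.** Section 8.5: the reason goes in the withdrawal part of the eCRF. Footnote h and Section 7.2: no AE entry. The event is then missing from the related-AE, intensity and discontinuation summaries of Section 13.2.3.3.1.
5. **The same reaction reported after the diary week.** Footnote h: AE entry, so it is counted in all those summaries.
6. **Reaction on the day of injection.** Table 2 footnote g and Section 9.2.1.1: staff inspect the site and record reactions in the eCRF. The eDiary rule does not apply. The protocol does not say whether these records also enter the AE tables.

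The exclusion in Section 11.1 settles case 3 for diabetes-related events by its SAE clause. Footnote h and Section 7.2 have no such clause, and nothing in the protocol gives a reason for the difference.

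The reach of the rule is 7 days × 3 injections = 21 days per patient, and 106 × 3 = 318 planned injections, of which 53 × 3 = 159 are placebo. These figures measure exposure to the rule. They do not say how many table entries would be wrong.

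**The case against.** A reader might infer that the AE tables will omit the treatment's main toxicity just when it is most likely to occur. The documents do not support that. Section 4.1.1 says that in the Phase IIa study site reactions followed a minority of injections, were mild, and came mainly on the day of injection, which is before the diary window opens. The same section says that influenza-like symptoms made up most of the AEs there.

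A reader might also infer that serious reactions go unreported. They do not: Section 11.6 captures every SAE on its own form, and the reconciliation in Section 12.1 would probably expose a missing AE entry.

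Nor are first-week reactions lost. They are a listed secondary safety endpoint (Section 6.4.2) and fall under the summary statistics planned for safety endpoints other than AEs. The rule applies alike to both blinded arms. Other clauses also push towards documentation. Section 8.5 wants withdrawals due to AEs fully documented, and Section 9.2.2 sends new conditions found at examination to the AE page. Finally, Section 5.1 reports no earlier withdrawals for these reactions, so few affected entries should be expected, although that experience was largely subcutaneous.

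All of this stands, and it limits the point. It does not remove it. The clauses that favour an AE entry are the ones the exclusion contradicts, and nothing says which prevails. A separate summary of reactions does not repair a discontinuation table that omits a discontinuation.

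**Conclusion.** The point holds in a limited form. Footnote h and Section 7.2 contradict Sections 10.4 and 11.5. They lack the SAE exception that Section 11.1 gives to a comparable exclusion, and they leave a serious first-week reaction with an SAE form but no AE entry. Followed literally, they keep a first-week diary-reported reaction that stopped the injections out of three planned AE summaries.

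The likely size is small and cannot be estimated from the protocol, which gives no rate for serious or treatment-stopping local reactions after intralymphatic injection. Even a single case would make the discontinuation row wrong.

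The conclusion rests on two assumptions: that the AE tables are built from the AE page of the eCRF, and that sites apply footnote h as written. If sites already enter such cases as AEs under Section 10.4 or 11.5, the tables are sound but the instructions still need reconciling.

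**What to change.** In footnote h and in Section 7.2, add after the exclusion: *unless the reaction meets the definition of an SAE or leads to study product being withheld or stopped, in which case it is also recorded as an AE (and as an SAE where applicable)*. In Section 11.5, refer to the exclusion so that routine reactions kept in the eDiary no longer contradict it, and check the result against Section 11.6. For a first-week reaction that prompts new medication, state whether Section 10.4 or the diary rule governs. A further trigger for severe but non-serious reactions is optional, since the protocol's own model in Section 11.1 excepts only SAEs.

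This changes recording only and leaves every rule on giving or stopping treatment as it is. The cost is one clause in two places, the cross-references and a few extra AE entries. Some reactions will appear in both the diary summary and the AE listings, which a footnote in the report can explain. Until the text is changed, the AE and discontinuation tables should be read together with the injection site reaction summary and the recorded reasons for stopping study product.
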